It is well established in the literature and in clinical practice that diminished blood flow to the extremities, as a result of peripheral artery disease (PAD) or otherwise, may impair wound healing and overall tissue viability [1-5]. PAD is labeled a “large personal, social, and economic burden in the United States” by the American Heart Association and American College of Cardiology. PAD is estimated to affect 8-10 million in the United States alone, while having a significant mortality rate (30% mortality in 5 years) [6, 7]. Over \$5B is spent annually treating peripheral vascular patients, the majority of which results from late diagnoses, ineffective interventions, and resulting lower limb amputations [8].

One end-stage manifestation of PAD is critical limb ischemia (CLI) [9, 10]. Generally, CLI is defined as: "any patient with chronic ischemic rest pain, ulcers, or gangrene attributable to objectively proven arterial occlusive disease" [9]. Early detection and treatment has the potential to keep PAD from reaching the point of CLI. Angiography is the gold standard for anatomical visualization of blood vessel structure and stenosis. However, angiographic information does not provide simple and functional metrics of blood flow, especially in the case of multiple stenoses. As such, the relationship between extremity blood flow and PAD/CLI cannot be elucidated without a more appropriate methodology for quantifying peripheral perfusion.

The ankle brachial index (ABI) is perhaps the most widely used screening technique to diagnose PAD. While the ABI is relatively simple to perform, it is a ratio of systolic blood pressures rather than a direct measurement of blood flow, and, despite its widespread usage, is only a proxy of direct perfusion measurements. Generally, a cutoff of ABI less than 0.91 is used to predict the presence of PAD, and a cutoff of ABI less than 0.4 is used to predict the presence of severe PAD indicating CLI [11].

While the noninvasive technologies mentioned above are considered standard of care in vascular medicine, there remains a lack of simple and continuous methods to assess PAD severity. A portable technology capable of quantifying disease severity simply and in real time could significantly ameliorate diagnosis, surgical treatment, and follow up care.

This study has many clinical implications. FlowMet-R is the first noninvasive technology to provide accurate and continuous quantification of microvascular perfusion. Hence, this technology may provide improved diagnostic and/or prognostic capabilities during procedures and in outpatient settings. The current study will set the foundation for future indications of FlowMet-R technology in vascular care.

The purpose of the investigation is to assess the efficacy of the FlowMet-R device in diagnosing PAD and CLI in patients scheduled for peripheral vascular examination. The results of the assessment of the FlowMet-R device will be compared to gold standard diagnostics including ABI, Toe Brachial Index (TBI), and Doppler Ultrasound.

4. Study Objectives

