5.2.2 Prior Clinical Studies

The FlowMet-R has been used previously as a non-significant risk device to study peripheral blood flow in five IRB-approved studies without adverse events. The first study ($n=37$) was a validation study performed at the University of California, Irvine (UCI IRB HS# 2006-4876). The protocol compared blood flow measurements during before, during, and after brachial artery occlusion using both the FlowMet-R and a laser Doppler system (Perimed Periflux). The study demonstrated a significant correlation between FlowMet-R and the laser Doppler systems (all trials showed $R > 0.7$). A second study ($n=47$)

aimed to correlate the FlowMet-R to the degree of wound in healing in patients with chronic wounds. This study was performed as Good Samaritan Hospital, San Jose CA (GSH FWA# 00006889). A third study (ongoing) at UCI (HS#: 2016-3286) is designed to measure blood flow dynamics in patients under anesthesia. A fourth study at the Vascular and Interventional Specialists of Orange County (VISOC) outpatient clinic in Orange, CA, collected correlative data between FlowMet-R, Rutherford category, ABI, and TBI in 100 patients (WIRB #1177294). A fifth study was conducted at the Cleveland Clinic, with results presented at ACC March 2018. The final two aforementioned studies found that FlowMet-R data could be used to produce a metric which is significantly correlated to TBI and ABI. In totality, these studies suggest that FlowMet-R measurement are correlated to existing standards used to assess vascular functionality and they provide evidence supporting the safety for FlowMet-R. No adverse events have been reported in any study.

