4.1.1.1.1 Definitions of PAD and CLI

- Two types of positive diagnosis of PAD will be explored according to published literature: (1) $ABI \leq 0.9$ or $ABI > 1.4$ and secondary verification of $TBI \leq 0.7$ with exhibition of at least mild claudication (Rutherford Category > 0), or (2) $ABI \leq 0.9$ or $ABI > 1.4$ and secondary verification of $TBI \leq 0.7$ without exhibition of symptoms. In either case, if the patient displays normal ABI but PAD is suspected, then a postexercise ABI will be performed using a 1-minute treadmill test or heel-raises. A postexercise drop of $ABI \geq 20\%$ or pressure drop $\geq 30\text{mmHg}$ will be considered a positive diagnosis [12].
- A positive diagnosis of CLI will be defined by exhibition of chronic rest pain and active wounds, verified by $TBI < 0.3$.
- Patients that are enrolled in the PAD positive cohort but are not positively diagnosed for PAD using the above definition (either because their disease is improving or they were screened incorrectly) will be considered PAD negative (see Section 7.11 for change to planned analysis).

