7.10 Evaluation of Objectives

7.10.1 Primary Objectives

The primary objectives will compare the 95% CI of the AUC from the ROC curve to a value of 0.5 at 0-, 3-, and 6-months for the two definitions of PAD and one definition of CLI using the acceleration time from the FlowMet-R device. The 95% CI will not be corrected for repeated measures within a participant. If the 95% CI of the AUC excludes 0.5 at all time points for PAD or CLI, the acceleration time from the FlowMet-R device will be considered predictive of the respective endpoint. The 95% CI of the AUC will be derived using the method described in DeLong, et al (1998) [15]. Note, the definition of PAD will be defined two ways and analyzed separately. Definitions of PAD and CLI are provided in Section 4.1.1.1.1.

Three supplementary summaries will be computed. The sensitivity and specificity will be computed by selecting the point on the ROC curve closest to the upper left corner. Accuracy will be computed as the number of limbs correctly diagnosed divided by the total number of limbs.

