7.10.2 Secondary Objectives

The secondary endpoints will be analyzed as follows:

1. The capability of the acceleration time from the FlowMet-R device to predict a vascular intervention or amputation will occur within three and six months following initial visit will be determined using the AUC from an ROC curve where the endpoint is vascular intervention or amputation within 7 months, which is the end of the 6 month follow-up window. The 95% CI of the AUC will be derived using the method described in DeLong, et al (1998) [15].
2. The capability of the acceleration time from the FlowMet-R device to predict a $\geq 50\%$ stenosis determined using the AUC from an ROC curve where the endpoint is vascular intervention or amputation within 7 months, which is the end of the 6 month follow-up window. The 95% CI of the AUC will be derived using the method described in DeLong, et al (1998) [15].
3. The correlations between the acceleration time from the FlowMet-R device and peripheral artery stenosis, changes in ABI, and changes in TBI will be computed using Pearson correlations. The changes for ABI and TBI will be as follows: 0 to 3 months, 0 to 6 months, and 3 to 6 months.
4. The correlation between the acceleration time from the FlowMet-R device and changes in Rutherford Classification will be computed using the Spearman correlation. The changes for Rutherford Classification will be as follows: 0 to 3 months, 0 to 6 months, and 3 to 6 months.

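### For stenosis and for intervention or amputation, the SAP gives an AUC for acceleration time alone, so the trial cannot say how the device performs beside ABI and TBI measured on the same limbs

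*SAP*

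**What the plan says.** **Purpose.** The SAP introduction, like Protocol 3.2, says "The results of the assessment of the FlowMet-R device will be compared to gold standard diagnostics including ABI"; the sentence continues with TBI and Doppler ultrasound. The introduction also says that "this technology may provide improved diagnostic and/or prognostic capabilities during procedures and in outpatient settings".

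**Primary analysis (SAP 7.10.1).** "The primary objectives will compare the 95% CI of the AUC from the ROC curve to a value of 0.5" at 0, 3 and 6 months. If 0.5 is excluded at every time point for PAD or CLI, "the acceleration time from the FlowMet-R device will be considered predictive of the respective endpoint". Under SAP 4.1.1.1.1, PAD rests on ABI ≤0.9 or >1.4 with TBI ≤0.7, or on a postexercise ABI. For CLI, "A positive diagnosis of CLI will be defined by exhibition of chronic rest pain and active wounds", with TBI <0.3 as verification.

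**Secondary analyses (SAP 7.10.2).** Item 1 concerns "The capability of the acceleration time from the FlowMet-R device to predict a vascular intervention or amputation" and gives an AUC with a DeLong interval. Item 2 announces ≥50% stenosis, but its endpoint text repeats intervention or amputation within 7 months. Neither item has a benchmark, a comparator or a success rule. Items 3 and 4 correlate acceleration time with stenosis and with changes in ABI, TBI and Rutherford class.

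**Status.** SAP 7.2 calls the objectives descriptive and not hypothesis-driven.

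**The concern.** ABI and TBI have two possible roles. In the primary analysis they are the reference, and tracking them is exactly what is being measured. For stenosis and for intervention or amputation they could be competing index tests, and there the plan leaves them out. It computes no AUC for ABI or TBI, no paired difference, and no model that adjusts for either.

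The protocol itself puts ABI in the second role. Protocol 3.1 quotes ABI's sensitivity (about 15% to 79%) and specificity (about 83% to 99%) for >50% stenosis, and describes duplex as the gold standard for judging it. A reader given an acceleration-time AUC for stenosis will want the TBI and ABI figures in the same limbs, and the planned output will not contain them.

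At stake is the interpretation of both secondary AUCs. A moderate value could mean that the device outperforms TBI, matches it, or is a weaker copy of it.

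**Working it through.** **1. What the plan's own figures are set against.** The sample-size text names no null value, so 0.5 is taken from SAP 7.10.1. The pilot AUC for CLI of 0.80 less the allowance of 0.2 gives 0.60. With 160 control limbs, two-sided alpha 0.05, power 0.80 and the Obuchowski binormal variance:

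- a = 1.414 × Φ⁻¹(0.60) = 0.358, so a² = 0.128; controls per case k = 160/100 = 1.6.
- V = 0.0099 × exp(−a²/2) × [(5a² + 8) + (a² + 8)/k] = 0.127.
- Cases = (1.960 + 0.842)² × V / (0.60 − 0.50)² = 7.85 × 0.127 / 0.01 ≈ 100.

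The CLI figure of 100 is reproduced (102 with the null variance, 108 to 110 with Hanley-McNeil). The claudication figure is not: AUC 0.67 − 0.05 = 0.62 needs 59 to 64 limbs, against 54 stated. The PAD total of 240 follows from neither assumption. So the one component that can be reproduced is sized against chance and not against another test.

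**2. What excluding 0.5 establishes for PAD and CLI.** The AUC detectable against 0.5 with 80% power is 0.582 (240 vs 160 limbs), 0.603 (100 vs 160) and 0.628 (54 vs 160). Meeting the rule shows agreement with the ABI/TBI-based diagnosis that is better than chance. It does not show close agreement.

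**3. Whether the comparison could be made.** ABI and TBI are scheduled at baseline, 3 and 6 months with the FlowMet recording (Protocol 9.2), on the same legs (Protocol 9.7), and SAP 7.7 already defines how their values are obtained. No new data are needed.

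**4. What a lone AUC can hide.** Assume a binormal model in which acceleration time has within-class correlation r with TBI and no information of its own. Its separation is then r times TBI's:

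- d(TBI) = √2 × Φ⁻¹(0.80) = 1.190
- AUC(acceleration time) = Φ(r × 1.190/√2) = Φ(0.8416 r)

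| r | AUC, acceleration time | Shortfall against TBI at 0.80 |
|---|---|---|
| 0.5 | 0.663 | 0.137 |
| 0.6 | 0.693 | 0.107 |
| 0.7 | 0.722 | 0.078 |
| 0.8 | 0.750 | 0.050 |

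**5. The same by simulation.** Assume 240 limbs, 30% events, TBI AUC 0.70 and independent limbs. Such an echo has a 95% CI excluding 0.5 in 74%, 94% and 99.6% of runs at r = 0.5, 0.7 and 0.9. A likelihood-ratio test of added value over TBI is positive in about 5%. Over a wider grid (events 15% to 45%, TBI AUC 0.65 to 0.80, r from 0.5 to 0.9) the ranges are 32% to 100% and 4% to 7%. Exclusion of 0.5 is only a yardstick here, since the SAP sets no rule for these endpoints.

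**6. What a paired comparison could show.** In 240 limbs, with events of 15% to 45% and marker correlation of 0.3 to 0.6 (all assumed), a paired DeLong test has power 0.47 to 0.94 for AUC 0.80 vs 0.70, and 0.17 to 0.37 for 0.75 vs 0.70. These figures treat limbs as independent and so are probably optimistic.

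**The case against.** The case for leaving the plan as it is has real force.

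- **The purpose sentence can be read as already fulfilled.** A gold standard is ordinarily what an index test is judged against, and the primary ROC does that. A head-to-head with ABI or TBI on PAD or CLI would be circular. This stands.
- **No superiority is claimed.** The wording on improved capability is conditional background text, no listed objective claims added value, and the plan is descriptive. This stands, and it limits how serious the gap is.
- **Earlier studies do not settle the matter.** Protocol 5.2.2 says that "FlowMet-R data could be used to produce a metric which is significantly correlated to TBI and ABI", but gives no coefficient, does not identify the metric as acceleration time, and is silent on stenosis and intervention. An echo of TBI is possible but not established.
- **The comparison would itself be biased, in both directions.** Entry on ABI/TBI criteria narrows their range, which favours the device. Clinicians have ABI and TBI when deciding on intervention, whereas Protocol 6.2 says FlowMet-R data will not change treatment; this favours TBI. Healthy limbs with normal ABI and TBI are assumed free of significant stenosis (SAP 5), so including them would favour ABI and TBI by construction. All three must be handled or stated.
- **A paired AUC difference cannot detect an echo.** Two markers with equal AUCs give a difference near zero whether or not they carry the same information. A model of added value is needed as well.

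Items 3 and 4 of SAP 7.10.2 offer a limited comparison with ABI and TBI. They do not show how either test performs for stenosis or intervention, so the gap remains.

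**Conclusion.** The point holds for two secondary endpoints. For ≥50% stenosis and for intervention or amputation, the SAP cannot say how acceleration time performs relative to ABI and TBI in the same limbs. For PAD and CLI there is no missing comparator, but the conclusion should be worded as agreement with an ABI/TBI-based diagnosis.

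Three stronger readings are tempting, and the documents do not support them:

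- That the trial cannot answer its stated purpose. Use of ABI and TBI as the reference is a fair meaning of the purpose sentence for PAD and CLI.
- That a copy of TBI would be declared prognostic. The rule for calling acceleration time predictive covers PAD and CLI only; the prognostic AUC could merely be read that way.
- That beating chance is close to assured. The cited earlier findings give no strength of correlation and concern other endpoints.

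The sizes above (AUC 0.66 to 0.75 for a marker that adds nothing to a TBI at 0.80) rest wholly on assumed inputs. They show what a lone AUC can conceal and do not estimate an error in this trial. The change is worthwhile because it is cheap and alters what can be concluded.

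**What to change.** In SAP 7.10.2:

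1. Correct item 2 so that its endpoint is ≥50% stenosis on imaging, and reconcile the threshold with SAP 4.1.2.1, which has >50%.
2. For items 1 and 2, add descriptive AUCs in the same limbs for baseline TBI (main comparator) and for ABI. Limit ABI to limbs with ABI ≤1.4, because both low and high values count as abnormal in the PAD definition.
3. Report the paired differences (acceleration time minus TBI; acceleration time minus ABI) with a 95% CI that allows for two limbs per patient, for example a clustered DeLong variance or a patient-level bootstrap.
4. Restrict the stenosis comparison to limbs with imaging.
5. Report a model with TBI, with and without acceleration time, to address added information.
6. State the limitations: entry selection on ABI/TBI, clinicians' access to ABI/TBI when deciding on intervention, and a study not sized to show small differences.
7. Present the results as estimates. Make no statement of improved capability from an acceleration-time AUC alone.

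In SAP 7.10.1, word the PAD and CLI conclusion as agreement with an ABI/TBI-based reference.

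The cost is SAP wording and a little more analysis of data already collected. The downside is that the comparison may be unfavourable to the device.

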4.1 Objectives

4.1.1 Primary Objectives

The primary objective of this study is to determine the efficacy of FlowMet-R measurements in diagnosing PAD and CLI. To accomplish this objective, FlowMet-R data (comprised of blood flow measurements and/or feature analysis of the blood flow waveform) will be used to create a predictive model of PAD severity. This model will then be used to generate diagnostic receiver operating characteristic (ROC) curves for PAD and, independently, CLI, at multiple time points. The following endpoints will be used to assess fulfillment of this objective.

4.1.1.1 Primary Endpoints

Employ a predictive model based upon FlowMet-R data to generate ROC curves for the diagnosis of PAD and, independently, CLI. ROC curves will be generated at the initial, three month, and six month time points, and will be used to compute the peak sensitivity, peak specificity, and area under the curve (AUC).

4.1.1.1.1 Definitions of PAD and CLI

- Two types of positive diagnosis of PAD will be explored according to published literature: (1) $ABI \leq 0.9$ or $ABI > 1.4$ and secondary verification of $TBI \leq 0.7$ with exhibition of at least mild claudication (Rutherford Category > 0), or (2) $ABI \leq 0.9$ or $ABI > 1.4$ and secondary verification of $TBI \leq 0.7$ without exhibition of symptoms. In either case, if the patient displays normal ABI but PAD is suspected, then a postexercise ABI will be performed using a 1-minute treadmill test or heel-raises. A postexercise drop of $ABI \geq 20\%$ or pressure drop $\geq 30\text{mmHg}$ will be considered a positive diagnosis [12].
- A positive diagnosis of CLI will be defined by exhibition of chronic rest pain and active wounds, verified by $TBI < 0.3$.
- Patients that are enrolled in the PAD positive cohort but are not positively diagnosed for PAD using the above definition (either because their disease is improving or they were screened incorrectly) will be considered PAD negative (see Section 7.11 for change to planned analysis).

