The ankle brachial index (ABI) is perhaps the most widely used screening technique to diagnose PAD. While the ABI is relatively simple to perform, it is a ratio of systolic blood pressures rather than a direct measurement of blood flow, and, despite its widespread usage, is only a proxy of direct perfusion measurements. Generally, a cutoff of $ABI < 0.91$ is used to predict the presence of PAD, and a cutoff of $ABI < 0.4$ is used to predict the presence of severe PAD indicating CLI [14]. In diagnosing >50% stenosis of lower limb arteries, researchers have found the ABI to have relatively high specificity, ranging from approximately 83%-99%, but highly variable sensitivity, ranging approximately 15%-79% [15]. In patients with partially non-compressible arteries, ABI values may be inflated and appear normal, despite the presence of significant disease. When the ABI is in a normal range but PAD is suspected, a postexercise ABI may be used to provide additional confirmation. A drop in >30mmHg ankle pressure or

ABI of >20% after exercise indicates the presence of significant disease [16]. The postexercise ABI may be performed with a treadmill test or repeated heel-raises [16].

While ABI has a relatively good sensitivity and specificity for claudication, recent data has shown that over 30% of patients with documented CLI have a normal ABI or ABI consistent with non-compressible blood vessels [17-19]. Therefore, in patients with wounds and/or gangrene, TBI is often used to assist in confirmation [20].

Color duplex ultrasound (CDU/CDI) imaging is often considered the gold standard when assessing arterial stenosis in a vascular laboratory, and good agreement has been shown between duplex and digital subtraction angiography (DSA) [21]. Generally, when assessing the performance of other diagnostic metrics such as ABI, Duplex ultrasound may be used as a gold standard to determine presence of >50% stenosis, indicating significant PAD [15, 22].

While the noninvasive technologies mentioned above are considered standard of care in vascular medicine, there remains a lack of simple and continuous methods to assess PAD severity. A portable technology capable of quantifying disease severity simply and in real time could significantly ameliorate diagnosis, surgical treatment, and follow up care.

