9.7.3 Postexercise ankle brachial index (ABI)

If an enrolled patient's ABI and TBI measurements classify that patient as not having PAD/CLI as per the definitions in Section 8.4, but it is suspected that the patient may have PAD based upon medical history or clinical symptoms, a postexercise ABI measurement will be performed. For such patients, guidelines

provided by the ACC/AHA will be followed. A treadmill or heel-raise test will be considered an acceptable challenge for measurement of postexercise ABI.

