5.5 Inclusion Criteria

Candidates for this study must meet all of the following inclusion criteria:

PAD Positive Cohort

- Subject meets PAD positive criteria set forth in Section 4.1.1.1
- Subject is willing and able to provide an informed consent.
- Subject is willing and able to comply with the study procedures.
- Subject is able to understand the study procedures.
- Subject is scheduled for vascular examination that includes noninvasive assessments as standard of care: ABI, TBI, and either a Duplex ultrasound or Angiogram.

Healthy Cohort

- Subject is willing and able to provide an informed consent.
- Subject is willing and able to comply with the study procedures.
- Subject is able to understand the study procedures.
- Subject has no history of positive PAD diagnosis and is not currently suspected of having PAD.

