Using a conservative estimation that the AUC for distinguishing PAD groups from healthy controls remains within $+/ - 0.05$ of the Claudicant group, and $+/ - 0.2$ of the CLI group, an estimate for the necessary sampling size can be determined. A standard type I error rate (α) of 0.05 and power of 0.8 is desired, thus the following approximate sample size was calculated [13,14]: 160 control limbs and 240 limbs with PAD, of which at least 54 limbs with Claudication and at least 100 limbs with CLI. Limbs with CLI may be included as a subset of limbs with PAD. A minimum of 250 patients (400 limbs) and maximum of 400 patients will be enrolled in the study.

7. Statistical Methods

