7.12 Changes to Planned Analysis

Patients will be classified based on definitions in Section 4.1.1.1.1 no matter the cohort they were originally enrolled in for the study.

8. Validation Requirements

To ensure the quality of the statistical results and datasets created for the study, the following validation requirements will be implemented. Programs that contribute directly or indirectly to the results pertaining to the primary and secondary objectives including TLG (Tables, Listings, and Graphs) development will be validated at least at level II by a statistician or a statistical programmer. Level I validation consists of a statistician or statistical programmer reviewer who independently programs output and then compares the output with that generated by the original statistician or statistical programmer according to the current work instruction. Level II: The peer reviewer reviews the code; where appropriate, performs manual calculations or simple programming checks to verify the output. Level III validation may be used for any previously validated program where only minor/administrative changes were made (e.g., change the location of the data directory). For level III validation, the original statistician or statistical programmer performs a visual inspection of the code and output to confirm functionality according to the current work instruction. Any results that are used for external publication or reports should be validated at levels I.

9. References

1. Mosely, L.H. and F. Finseth, Cigarette smoking: impairment of digital blood flow and wound healing in the hand. *The Hand*, 1977(2): p. 97-101.
2. Stadelmann, W.K., A.G. Digenis, and G.R. Tobin, Impediments to wound healing. *The American journal of surgery*, 1998. 176(2): p. 39S-47S.
3. Cronberg, C., et al., Peripheral arterial disease. *Acta Radiologica*, 2003. 44(1): p. 59-66.
4. Ouriel, K., Peripheral arterial disease. *The lancet*, 2001. 358(9289): p. 1257-1264.
5. Falanga, V., Wound healing and its impairment in the diabetic foot. *The lancet*, 2005. 366(9498): p. 1736-1743.
6. Norgren, L., et al., Inter-society consensus for the management of peripheral arterial disease (TASC II). *European Journal of Vascular and Endovascular Surgery*, 2007. 33(1): p. S1-S75.

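### The PAD and CLI reference definitions are not nested: a CLI limb with a normal resting ABI can be a case on the CLI curve and a PAD-negative on the primary PAD curve, and the two postexercise triggers disagree on whether it gets a second test

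*SAP*

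**What the plan says.** **PAD.** Protocol and SAP 4.1.1.1.1 give two definitions with the same haemodynamic core. The first reads "1) $ABI \leq 0.9$ or $ABI > 1.4$ and secondary verification of $TBI \leq 0.7$ with exhibition of at least mild claudication". The second has the same ABI and TBI terms without symptoms. TBI confirms an abnormal ABI and does not make a limb PAD-positive by itself.

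**Second route.** The same section adds: "if the patient displays normal ABI but PAD is suspected, then a postexercise ABI will be performed using a 1-minute treadmill test or heel-raises". An ABI drop of at least 20% or a pressure drop of at least 30 mmHg then counts as positive.

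**CLI.** Chronic rest pain and active wounds, verified by TBI below 0.3. There is no ABI term.

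**Classification.** SAP 4.1.1.1.1 makes PAD-cohort patients who do not meet the PAD definition PAD-negative. SAP 7.12 adds: "Patients will be classified based on definitions in Section 4.1.1.1.1 no matter the cohort they were originally enrolled in for the study".

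**Counting.** SAP 5.3 and Protocol 8.1 ask for more than 100 CLI limbs within the 240 PAD limbs. SAP section 6 says: "Limbs with CLI may be included as a subset of limbs with PAD".

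**Postexercise trigger in Protocol 9.7.3.** "If an enrolled patient's ABI and TBI measurements classify that patient as not having PAD/CLI as per the definitions in Section 8.4", and PAD is still suspected, the test is done.

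**Inclusion.** SAP 5.5 requires: "Subject meets PAD positive criteria set forth in Section 4.1.1.1".

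**The concern.** Protocol 3.1 itself warns that "over 30% of patients with documented CLI have a normal ABI or ABI consistent with non-compressible blood vessels", and says that TBI is used for confirmation in patients with wounds or gangrene for that reason. The PAD reference standard nevertheless leaves ABI as the gate. Some of the most ischaemic limbs in the study can then be labelled PAD-negative. If the device ranks such a limb as severely diseased, it is right on the CLI curve and wrong on the PAD curve, and both curves are primary. The error runs one way: it lowers the PAD AUC and the apparent specificity for a reason unrelated to the device.

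The two postexercise triggers make this worse. If sites apply them differently, the label of the same kind of limb depends on the site.

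**Working it through.** **1. The rules applied to one limb.** Take TBI 0.25, rest pain and an active wound (Rutherford category 5), and vary the resting ABI. The result is the same whether the PAD rule is read as (ABI low or high) and TBI, or as ABI low or (ABI high and TBI).

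| Resting ABI | CLI | PAD at rest (definition 1) |
|---|---|---|
| 0.35, 0.90 | positive | positive |
| 0.95, 1.10, 1.40 | positive | **negative** |
| 1.50 | positive | positive |

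The gap is ABI above 0.9 and up to 1.4. Limbs with ABI above 1.4 are captured.

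**2. Does the postexercise route close the gap?** Under SAP 4.1.1.1.1 it can: a normal ABI with suspected PAD leads to the test. Under Protocol 9.7.3 read literally it does not, because a patient classified as CLI is not one classified as having neither condition. No sentence in either document makes a CLI limb PAD-positive.

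**3. The plan's own CLI figure.** Inputs from SAP section 6: AUC 0.80 − 0.20 = 0.60 against 0.5, α 0.05 (taken as two-sided), power 0.80, and 160/100 = 1.6 controls per CLI limb. With the Obuchowski binormal variance, V = 0.0099·exp(−A²/2)·[(5A² + 8) + (A² + 8)/1.6] and A = 1.414·Φ⁻¹(AUC), V is 0.1287 at 0.5 and 0.1274 at 0.60.

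n = (1.960·√0.1287 + 0.842·√0.1274)² / 0.10² = 100.7, so 101 CLI limbs and 162 controls. This matches the planned 100 and 160.

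**4. Size of the effect at baseline.** Inputs: pilot AUCs of 0.67 (claudication) and 0.80 (CLI), 160 controls, and 240 PAD limbs taken as 140 non-CLI and 100 CLI. Assumptions: equal-variance binormal model, and m CLI limbs with a normal ABI and no positive postexercise test.

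- Distance from controls: √2·Φ⁻¹(0.67) = 0.622 and √2·Φ⁻¹(0.80) = 1.190.
- Claudication against CLI: Φ((0.622 − 1.190)/√2) = 0.344. CLI against CLI: 0.5.
- AUC(m) = [140·(160·0.67 + 0.344m) + (100 − m)·(160·0.80 + 0.5m)] / [(240 − m)(160 + m)]

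| m | AUC | Hanley-McNeil 95% CI | AUC if 240 positives are kept |
|---|---|---|---|
| 0 | 27,808/38,400 = 0.724 | 0.675–0.773 | 0.724 |
| 10 | 27,460/39,100 = 0.702 | 0.652–0.753 | 0.706 |
| 20 | 27,011/39,600 = 0.682 | 0.631–0.734 | 0.689 |
| 30 | 26,463/39,900 = 0.663 | 0.611–0.716 | 0.674 |

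The last column keeps 140 non-CLI and 100 CLI positives and adds m CLI limbs to the negatives, because enrolment continues until 240 PAD limbs are measured.

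**5. Follow-up, as illustration.** Healthy subjects are measured once, and the SAP does not say whether their data are reused at 3 and 6 months. Suppose they are not, and the only other PAD-negatives are 20 non-CLI limbs that have improved to healthy values:

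AUC(m) = [120·(20·0.67 + 0.344m) + (100 − m)·(20·0.80 + 0.5m)] / [(220 − m)(20 + m)]

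This gives 0.73 for m = 0, 0.62 (95% CI 0.52–0.72) for m = 10 and 0.56 (0.47–0.66) for m = 20. The figure of 20 improved limbs is invented for the illustration.

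**The case against.** **The postexercise route.** Rest pain, a wound and a very low TBI raise suspicion of PAD, so under SAP 4.1.1.1.1 the limb may be tested and become PAD-positive. Protocol 9.7.3 is also loosely drafted: CLI cannot be classified from ABI and TBI alone, and the section it cites for definitions, 8.4, holds the exclusion criteria. This stands. A reader might infer that every such limb stays PAD-negative, but only a literal reading of 9.7.3 gives that.

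**Exclusion and mislabelling.** A reader might infer that these patients both fail inclusion and count as PAD-negatives. At baseline the two normally exclude each other, since a patient who is not enrolled is on no curve. Both apply only if the patient enters through the other limb or is screened incorrectly. Failure of inclusion is itself uncertain, because the SAP section cited for the PAD criteria also contains the CLI definition.

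**The 30% figure.** It combines normal with non-compressible ABI, and it describes documented CLI in general, not CLI as this study defines it. It cannot serve as the normal-ABI share.

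**A PAD AUC driven to 0.5 or below.** A reader might infer this, but the baseline range does not support it: the worst case is 0.663, with a lower limit of 0.611.

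**Nesting.** The subset wording in SAP section 6 is permissive, and the target in 5.3 could be met by limbs that satisfy both definitions. So the documents do not state that every CLI limb is a PAD limb. They do count CLI limbs among PAD limbs and give no rule for one that fails the PAD definition.

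**Descriptive reporting.** SAP 7.2 says the objectives are not hypothesis-driven. But 7.10.1 still calls the measure predictive only if the CI excludes 0.5 at every time point, so the labels matter.

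**Conclusion.** The concern holds as a defect in the reference classification. A limb with resting ABI above 0.9 and up to 1.4 that meets the CLI definition is PAD-negative in the primary PAD ROC unless a postexercise test is done and positive, and the two documents disagree on when that test applies.

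The baseline effect is a downward-biased PAD AUC: from 0.724 to between 0.702 and 0.663 for 10 to 30 misplaced limbs, or to between 0.706 and 0.674 if 240 PAD-positive limbs are kept. Apparent specificity falls as well. The comparison with 0.5 does not change at baseline.

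These figures rest on an assumed number of affected limbs, an equal-variance binormal model, and pilot AUCs from a fitted model; the SAP analyses acceleration time, which may behave differently. At 3 and 6 months the effect could be larger, and could alter the conclusion, if the healthy controls are not reused. That depends on a choice the SAP does not state.

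**What to change.** **Analysis classification.** In SAP 4.1.1.1.1 and 7.12, state that for the PAD ROC a limb meeting the CLI definition at a visit is not counted as PAD-negative, and is classified as PAD-positive under definition 1 whatever its resting ABI. This agrees with the subset wording in SAP 5.3 and section 6. Report the literal ABI-gated classification as a sensitivity analysis, with the number of limbs whose label differs at each visit.

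**Reconciliation.** The sponsor must reconcile 4.1.1.1.1 with Protocol 9.7.3 on when the postexercise test applies. SAP 5.5 must be reconciled with the Protocol synopsis and 8.3, which point to 8.4 and 8.3 for criteria that neither section contains, on whether a patient who meets only the CLI definition satisfies the PAD inclusion criterion. Which clinical rule to adopt is for the sponsor.

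**Cost.** The SAP change is a sentence or two plus one repeated analysis. ABI, TBI, Rutherford category and wound status are already collected. Any protocol change needs IRB approval before use (Protocol 14.6). A small downside is that the PAD reference for these limbs would rest on TBI and symptoms and not on ABI; the sensitivity analysis shows how much depends on that.
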